## 9.6 Discontinuation of Therapy

Reasons for permanent discontinuation include the following:

1. In patients with CIS at baseline, failure to clear CIS lesions by Week 12; however, patients who clear CIS lesions but have low-grade disease should continue to be treated. Patients with CIS lesions that fail to clear may be followed by cystoscopy until they have a cystectomy or start an alternative treatment, but will be considered non-responders in the primary efficacy analysis
2. Recurrence of high-grade papillary lesions at the Week 12 cystoscopy or later or of CIS lesions after clearance. ***Only patients who meet the definition of recurrence should be discontinued. Patients with persistence or appearance of lower grade disease should not be discontinued***
3. Unacceptable toxicity, defined as a persistent Grade 3 AE or higher despite dosing delay (according to the AE management guidelines in Section 9.5)
4. Withdrawal of consent

Any patient without tumor in the bladder but presence of tumor in the upper urinary tract will not be classified as a failure in primary analyses and will continue study participation.

The reason for early discontinuation must be documented in the electronic case report form (eCRF). After discontinuation of study treatment for any reason, patients should be followed up for 30 days to assess safety.

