#### **9.4.3 Maintenance Treatment**

Upon completion of the induction phase, patients will transition to a maintenance therapy schedule of BC-819 (ie, once every 3 weeks). The first maintenance treatment and visit will occur 12 weeks after enrollment (Visit 11). Treatments will continue every 3 weeks for 84 additional weeks until the end of the study (end of study [EOS] Visit 39) at 96 weeks.

Patients who have recurred with high-grade papillary carcinoma or with metastatic disease will be considered treatment failures and will be withdrawn from the study. All suspected recurrences (by direct visualization) must be documented by biopsy results.

Patients who are free of high-grade tumors or who are tumor-free (ie, patients benefiting from treatment) will be allowed to continue to receive maintenance therapy every 3 weeks per the schedule of treatment during the maintenance phase ([Table 12.2](#) and [Table 12.3](#)) as long as response status is maintained and they are not considered a treatment failure.

Patients will undergo repeat direct visualization (ie, cystoscopy  $\pm$  biopsy and cytology) and re-TUR (as needed for cause) every 12 weeks during the first and second year of the study.

All enrolled patients will complete the following quality of life questionnaires at the visits indicated in the study schedule ([Table 12.1](#) and [Table 12.2](#)):

- The European Organization for Research and Treatment of Cancer quality of life Questionnaire (EORTC QLQ-C30; a general questionnaire for cancer)
- Quality of Life Questionnaire–Non-Muscle-Invasive Bladder Cancer Questionnaire (QLQ-NMIBC24; a specific questionnaire for NMIBC disease)

The end of the study will be the 96-week visit (Visit 39) for all patients.

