## 12. STUDY PROCEDURES AND FLOWCHARTS

The administration of BC-819 is separated into 2 phases, the induction phase and the maintenance phase.

During the induction phase, eligible patients will receive BC-819 once per week for 10 consecutive weeks. The flow chart for the induction phase is [Table 12.1](#).

During the maintenance phase, patients will transition to once every 3 weeks administration of BC-819 and will be evaluated every 12 weeks by cystoscopy for staging of response in order to determine continued participation. The urine cytology and cystoscopy must be completed within 14 days prior to the next administration of BC-819 and fully evaluated before initiating the treatment. The flow charts for the maintenance phase are [Table 12.2](#) and [Table 12.3](#).

In each of the the study flow charts, a study week is defined as 7 days. A description of each procedure is in Section [12.1](#). End of study procedures are required within 4 weeks of leaving the study.

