### 13.3 Subject Disposition

The number of patients who complete and who do not complete the study will be summarized. Reasons for patients not completing the study will be categorized as follows:

- Adverse event:
  - Related to study medication
  - Related to study procedure
  - Unrelated to either study medication or procedure
- For patients with CIS at baseline, failure to clear CIS lesions by the 12-week cystoscopy. These patients can be followed by cystoscopy in the study until they begin an alternative treatment or undergo cystectomy
- Recurrence: recurrence requiring discontinuation from the study (see Section 9.6)
- Death from any cause (with specification of cause of death)
- Withdrawal of consent

- Loss to follow-up
- Other (with specification of reason)

The primary reason for discontinuation will be listed. Thus, if a patient discontinues therapy because of an AE and subsequently dies, the reason for discontinuation will be listed as AE.

As etiology of AEs is often uncertain, more than 1 reason for an AE resulting in discontinuation (eg, both BC-819 and study procedure [catheterization]) may be listed as causes, although the primary reason for discontinuation will be AE.

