7.3.2.3 Overall Survival

OS is defined as the time first dose of study medication until death. Kaplan-Meier methods will be used to estimate the OS (ie, percent surviving without death) and the 95% confidence interval at 48, 72, and 96 weeks in all patients in the FAS and the subgroup of patients with CIS. The median OS and its 95% confidence interval will also be estimated. Kaplan-Meier plots for OS will be created.

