7.3.2.4 Quality of Life

Quality of life will be assessed using the EORTC QLQ-C30 (a general questionnaire for cancer) and the QLQ-NMIBC24 (a specific questionnaire for NMIBC disease). The questionnaire is administered at baseline (Day 1) and Weeks 21 and 45 prior to any clinical measurements, assessments, evaluations, or procedures being performed.

The QLQ-C30 is composed of both multi-item scales and single-item measures. These include five functional scales (physical, role, emotional, cognitive, and social), three symptom scales (fatigue, nausea and vomiting, and pain), a global health status/quality of life scale, and six single items (dyspnea, insomnia, appetite loss, constipation, diarrhea, and financial difficulties). Each of the multi-item scales includes a different set of items and no item occurs in more than one scale.

Each scale will be summarized on a 0-100 scale according to the scoring manual ([Fayers](#)). For functional scales and the global health status/quality of life scale, a higher score corresponds to greater function or quality of life. For symptom scales, a higher score corresponds to greater symptom burden.

This document is confidential.

The QLQ-NMIBC24 is composed of both multi-item scales and single-item measures related to NMIBC. These include five multi-item symptom scales (urinary symptoms, malaise, future worries, bloating and flatulence, and male sexual problems), one multi-item functional scale (sexual function) and five single-item measures (intravesical treatment issues, sexual intimacy, risk of contaminating a partner, sexual enjoyment, and female sexual problems).

Each scale in the QLQ-NMIBC24 will be summarized on a 0-100 scale similar to the scoring described for the QLQ-C30 ([Fayers](#); [Blazebury](#)). For functional scales (sexual function and sexual enjoyment), a higher score corresponds to greater function or quality of life. For symptom scales, a higher score corresponds to greater symptom burden.

Each scale from the two questionnaires will be summarized descriptively at baseline and the subsequent visits using the actual score at the visit and the change from baseline at the visit. Means, standard deviations, medians, range, and the 95% confidence interval for the mean will be summarized.

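### No progression, survival or QoL follow-up is required after treatment stops, so 48- to 96-week PFS and OS rest on informative censoring and post-baseline QoL reflects only patients still on study

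*Protocol*

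**What the plan says.** **Stopping.** Protocol 9.6 lists as a reason for permanent discontinuation: "In patients with CIS at baseline, failure to clear CIS lesions by Week 12". Under Protocol 9.4.3, patients with high-grade papillary recurrence or metastatic disease "will be considered treatment failures and will be withdrawn from the study".

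**After stopping.** Two things are required. Protocol 9.6: "After discontinuation of study treatment for any reason, patients should be followed up for 30 days to assess safety". Protocol 12: "End of study procedures are required within 4 weeks of leaving the study". One thing is permitted. Protocol 9.6: "Patients with CIS lesions that fail to clear may be followed by cystoscopy until they have a cystectomy or start an alternative treatment"; Protocol 13.3 repeats it: "These patients can be followed by cystoscopy in the study until they begin an alternative treatment or undergo cystectomy". Tables 12.1 to 12.3 contain no off-treatment contact.

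**What is to be estimated.** SAP 7.3.2.3 asks for Kaplan-Meier OS and "the 95% confidence interval at 48, 72, and 96 weeks in all patients in the FAS", and also for the CIS subgroup. SAP 7.3.2.2 does the same for PFS. SAP 7.3.2.1 adds overall proportions with T2 or greater or metastatic disease, cystectomy and death. Time to progression is censored at the last progression-free assessment; no censoring rule is given for OS, although SAP 7.3.2 lists a last-contact date.

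**QoL.** SAP 7.3.2.4: "The questionnaire is administered at baseline (Day 1) and Weeks 21 and 45". Neither Week 12 nor the end-of-study column of Table 12.3 has a QoL assessment, although Protocol 12.1 cites Table 12.3 for it.

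**The concern.** Kaplan-Meier estimates are valid only if patients censored at a given time have the same later risk as those who remain. Here patients leave because the disease persisted or came back. The protocol itself argues that this matters: Section 7.5 ranks high-risk recurrence first among the predictors of progression, and Section 7.1.1 says that mortality rises considerably once the disease becomes invasive. Censoring is therefore tied to the outcome, and the later part of each curve takes its hazard from patients who are doing well.

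At stake is how the 48- to 96-week PFS and OS read. They would be presented as results for all treated patients, but would carry almost no information on what happened to those in whom treatment failed. The SAP's overall counts of progression, cystectomy and death would miss events after withdrawal for the same reason. QoL has a similar gap: a patient who stops at Week 12 has a Day 1 score and no change score.

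**Working it through.** **1. The design's own figures.** Protocol 13.1 gives power for an exact test against 20% at two-sided 0.05.
- n = 70, CR 40%: at least 22 CRs are needed and power is 94.5% (stated: over 95%).
- n = 100, CR 35%: at least 29 CRs are needed and power is 91.5% (stated: about 92%).

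The first falls just short of the stated figure. Both are close enough to confirm 35% and 40% as the design CR rates.

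**2. How many are non-responders?** Share = 1 − CR rate.
- CR 40%, 70 CIS patients: 0.60 × 70 = 42; 42/140 = 30% of all patients.
- CR 35%, 100 CIS patients: 0.65 × 100 = 65; 65/140 = 46% of all patients.

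The probability that more than half of CIS patients have no CR is 94% in the first case and 99.9% in the second. These are shares with no CR through Week 48. They become departures near Week 12 only if 9.6 is applied as written. The footnote to Table 12.2 makes response assessment mandatory at Weeks 24, 36 and 48 in CIS patients with no CR yet, which implies that some stay. The two places must be reconciled.

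**3. Size of the bias in Kaplan-Meier.** Assumptions, none of them in the documents: exponential hazards, 96-week event-free probabilities R (continuing patients) and F (failures), and failures censored at about Week 16 (Week 12 plus about 30 days). With failure share w:
- True value = (1 − w)R + wF
- Kaplan-Meier = [(1 − w)R^(16/96) + wF^(16/96)] × R^(80/96)

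Worked case, CIS patients, w = 0.60, R = 0.95, F = 0.80:
- True = 0.4 × 0.95 + 0.6 × 0.80 = 0.860
- To Week 16: 0.4 × 0.9915 + 0.6 × 0.9635 = 0.9747
- Kaplan-Meier = 0.9747 × 0.9582 = 0.934, an excess of 7.4 points

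Excess at Week 96, in points:

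| R, F | CIS, w = 0.60 | CIS, w = 0.65 | All 140, w = 0.30 | All 140, w = 0.46 |
|---|---|---|---|---|
| 95%, 90% | 2.5 | 2.7 | 1.2 | 1.9 |
| 95%, 80% | 7.4 | 8.0 | 3.7 | 5.7 |
| 90%, 70% | 9.8 | 10.6 | 4.9 | 7.6 |
| 95%, 95% | 0 | 0 | 0 | 0 |

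The all-patient columns count only CIS non-responders as leaving; later recurrences, including those in papillary-only patients, are not modelled. The result is not sensitive to the censoring week. In the worked case, censoring at Week 12 gives 0.9809 × 0.9561 = 0.938 instead of 0.934.

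**4. QoL.** The post-baseline visits are Weeks 21 and 45. A patient who stops at Week 12 contributes to neither, and the end-of-study procedures include no questionnaire.

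**The case against.** The strongest reply is that these are descriptive secondary endpoints with no hypothesis test, that the primary CR analysis does not depend on them, and that the bias figures rest on risks the documents do not supply. All of that stands. It limits the weight of the point but does not remove the gap: no section requires the missing data to be collected.

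Several stronger readings are tempting, and the documents do not support them.

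- A reader might infer that late PFS and OS describe responders only. They do not. Failures are in the FAS and in the risk set until censored, and their early events count. In addition, 40 to 70 papillary-only patients (140 minus 100 or 70) have no CR endpoint and stay while free of high-grade recurrence.
- A reader might infer that follow-up is 30 days and nothing else. Cystoscopy of Week 12 CIS failures may continue, and end-of-study procedures are required. But the cystoscopy is optional, stops at cystectomy or new therapy, and is not a survival or QoL follow-up.
- A reader might infer that all QoL results are affected, or that at least 60% of CIS patients have no post-baseline QoL. Day 1 covers everyone, and Week 21 includes papillary-only patients still on study and Week 12 responders who recur later. The 60% is an expected non-CR share through Week 48 at one assumed rate, not a floor and not a Week 12 count.
- A reader might infer that this gap prevents the study from showing whether delayed cystectomy led to progression. A single arm without an immediate-cystectomy comparator could not show that even with complete follow-up.

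The Week 16 censoring time is also an inference, since the SAP states no OS rule and optional cystoscopy could extend the progression data.

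**Conclusion.** The point holds in this form: nothing beyond 30 days of safety follow-up and end-of-study procedures is required after discontinuation, so 48- to 96-week PFS and OS in the FAS and the CIS subgroup depend on informative censoring and are probably too high. The direction follows from the protocol's own account of recurrence and progression. The size does not: about 2.5 to 10 points at Week 96 in CIS patients, and roughly 1 to 8 points overall, hold only under the assumed risks and early censoring of failures, with no bias if the two groups have equal risk. Post-baseline QoL change describes patients still on study. The matter should be corrected, because follow-up not collected may not be recoverable, but it does not touch the primary endpoint.

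**What to change.** - **Follow-up.** Amend Protocol 9.6 so that patients who stop treatment, unless they withdraw consent, have a remote status check (telephone or record review, no study procedures) about every 12 weeks to Week 96 from first dose. Record vital status, T2 or greater, nodal or metastatic disease, cystectomy with stage, and new bladder cancer therapy.
- **Analysis.** Use these data in SAP 7.3.2.2 and 7.3.2.3, and state the OS censoring rule.
- **QoL.** Add both questionnaires to the end-of-study or early-discontinuation visit, and to Visit 11 if wanted. Do not require that they precede the cystoscopy result at Visit 11: Protocol 12 has cystoscopy and cytology fully evaluated before that dose, so the result would normally be known.
- **Consistency.** Reconcile 9.6 with the Table 12.2 footnote on patients who have no CR yet.
- **If follow-up is not added.** Label the 48- to 96-week PFS and OS as on-study estimates subject to informative censoring, and add a sensitivity analysis that varies the later risk of patients who left.

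Cost: a protocol and consent amendment, one eCRF page, brief calls or chart checks, and one or two extra questionnaires per patient. No sample-size figure changes.

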## **10. STUDY PRODUCT**

### **10.1 Study Medication Supply**

BC-819 will be supplied by the study sponsor.

Study product is manufactured in accordance with current good manufacturing practices; the recombinant plasmid of BC-819 is manufactured by Boehringer-Ingelheim RCV, Vienna, Austria, and the transfection agent (PEI) by ChemCon GmbH, Freiburg, Germany.

### **10.2 Description of Study Product**

BC-819 vials contain a 5- mL dose of BC-819 at a concentration of 0.4 mg plasmid/mL in 5% trehalose solution.

### **10.3 Packaging and Labeling**

BC-819 is supplied as a single ready-to-use vial containing 50 mL BC-819 active plasmid and transfection agent complex at a concentration of 0.4 mg plasmid/mL in 5% trehalose solution. The product will be labelled according to local and national regulatory requirements.

### **10.4 Conditions for Storage and Use**

BC-819 must be stored in a temperature-controlled and monitored environment at 2°C to 8°C.

### **10.5 Method of Assigning Patients to Treatment Groups**

This is a single-arm study. All patients will receive BC-819 according to the schedules shown in Section 12 (Table 12.1, Table 12.2, and Table 12.3).

### **10.6 A Dispensing, Compliance and Accountability**

All study medications will be administered in the clinic under the supervision of the investigator or his/her delegate. Accordingly, compliance and accountability will be assessed from records of administration maintained by the investigational study team at each site.

The investigator is responsible for maintaining accountability for the receipt, dispensing, and return of all study medication. Maintenance of all required investigational medicinal product (IMP) records can be delegated by the investigator to a suitably qualified member of the investigational study team at each site.

### **10.7 Concomitant Therapy**

Patients may not receive other therapy for bladder cancer, either intravesical or systemic, except for anticholinergic treatment and/or chronic use of corticosteroids.

Patients may receive therapy for AEs per investigator judgment.

All concomitant medications, whether for TEAEs or other reasons, and the indications for their use must be recorded in the patient's eCRF.

## 11. EFFICACY AND SAFETY ASSESSMENTS

### 11.1 Primary Efficacy Variable

The primary efficacy endpoint is, in patients with CIS at baseline, the:

- Proportion that achieves a CR at any time on or after week 12 and within the first 48 weeks

Complete response is defined as at least one of the following:

- Negative cystoscopy and negative (including atypical) urine cytology
- Positive cystoscopy with biopsy-proven benign or low-grade NMIBC and negative cytology
- Negative cystoscopy with malignant urine cytology if cancer is found in the upper tract or prostatic urethra and random bladder biopsies are negative

The complete response in patients with CIS for this endpoint must be documented on or after the Week 12 response assessment and on or prior to the Week 48 assessment. Duration of complete response in patients with CIS will be calculated from the documented onset of the complete response to the assessment where the patient no longer meets the definition of complete response. More generally, recurrence is defined as the reappearance or persistence of high-grade disease, or new high-grade disease. Recurrence must be biopsy proven. Persistence, appearance, or presence of lower grade disease will not be considered recurrence.

### 11.2 Secondary Efficacy Variables

The secondary endpoints include the following:

- The incidence of EFS at 48 weeks, where EFS is defined as high-grade recurrence-free survival (overall population and subgroup of patients with CIS)
- The incidence of EFS at 12, 24, 36, 72, and 96 weeks, where EFS is defined as high-grade recurrence-free survival (overall population and subgroup of patients with CIS)
- Time to recurrence; recurrence is defined as an EFS event
- The incidence of PFS at 48, 72, and 96 weeks as well as time to progression estimated using Kaplan-Meir methods. Progression is defined as the development of T2 or greater disease. Sensitivity analyses will also be performed and will include any of the following as progressions:
  - An increase in stage from Ta or CIS to T1, or
  - Development of T2 or greater, or
  - Lymph node disease, or
  - Distant metastasis
- Overall survival of patients enrolled in the study at 48, 72, and 96 weeks and survival time estimated using Kaplan-Meier methods

- Changes in quality of life over time, as measured by the EORTC QLQ-C30 (a general questionnaire for cancer) and the QLQ-NMIBC24 (a specific questionnaire for NMIBC disease)

Additionally, patients with appearance of new high-grade disease (ie, new high-grade papillary disease in patients with CIS only or new CIS in patients with papillary disease only) will be classified as treatment failures in EFS analyses, as will patients with CIS at baseline whose CIS lesions have not resolved by the 12-week cystoscopy, or who have recurrent CIS at later cystoscopies.

At each follow-up visit, response of existing lesions and presence of any new lesions will be evaluated (by direct visualization and biopsies as needed) and reported in the eCRF. Recurrences must be proven and documented by biopsy.

A biopsy will be performed at screening and when indicated by direct visualization at other visits for purposes of staging and grading.

The laboratory results from pathology specimens (samples taken from re-TUR of tumors) will be reviewed by the study investigator. These laboratory results will be provided to the investigator from the certified and/or accredited laboratory local to the site, where the samples were processed. If there is no certified and/or accredited laboratory on site, the specimen may be shipped to another agreed upon certified and/or accredited laboratory for analysis and reporting of results to the study investigator. There is no central laboratory review and/or evaluation requirement in this study. For these efficacy analyses, recurrence will be considered biopsy proven and/or sufficiently documented following a local investigative pathology review that deems the specimen as positive.

In the case where a patient consistently has positive cystoscopy or cytology results (3 or more) but repeated negative biopsy, the patient will not be considered a treatment failure for the EFS analyses.

### **11.3 Safety Variables**

The safety endpoint is occurrence of AEs according to CTCAE version 5.0, regardless of relationship to study medication.

#### **11.3.1 Clinical Laboratory**

Standard clinical chemistry, hematology, and urinalysis assessments will be conducted periodically during the study at the hospital facilities. Abnormalities that develop after the start of study medication and abnormalities present at baseline, but which worsen by at least 1 CTCAE grade on study will be considered AEs when clinically significant. Investigator discretion is allowed in determination of AEs, and investigators will assess grade, severity, and causality of any abnormalities considered AEs.

